### 6.5 SAFETY

Subject will be included in the safety group if they are in the ITT analysis population and study treatment was at least attempted. This is the primary analysis population for safety, including adverse events (this is a change from the protocol, where it states that adverse events will be reported on all enrolled patients; it has been since felt that this could underreport the true adverse event rates in patients to whom randomized treatment was attempted). Patients are analyzed under the treatment received.

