12.2 Analysis Populations

12.2.1 All Enrolled

Any subject who has signed informed consent will be included in the all enrolled population. Should a subject be considered a screen failure, the reason for failure will be documented, and the subject will be exited from the study. Adverse events will be reported for all enrolled subjects through the time of study exit.

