12.2.2 Intent-to-Treat (ITT)

The intent-to-treat population (ITT) will consist of any subjects that have signed the ICF, meet study eligibility criteria, and are randomized to the treatment or control arm of the study.

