### 6.2 INTENT TO TREAT POPULATION (ITT)

The intent-to-treat (ITT) population for this study includes subjects that are enrolled in the study, have signed the ICF, meet study eligibility criteria, and have been randomized to either the treatment or control arm of the study.

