## 7.4 PROTOCOL VIOLATIONS

A protocol violation is a failure to comply with the requirements specified within this clinical study protocol. Protocol violations will be summarized in the CSR. This summary will include the number and percent of subjects (overall and by site) with each violation type for the ITT analysis set. Protocol violations, according to section 14.2 of the protocol and the Protocol Deviation CRF, include:

- Failure to obtain subject's informed consent prior to any study-related activities;
- Subject did not meet the inclusion and/or exclusion criteria and were enrolled;
- Failure to conduct protocol required clinical test or assessment;
- Failure to complete protocol required assessments within the required time frame
- Failure to perform assessment or test according to the protocol
- Failure to report serious adverse events according to protocol requirements.

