## 10 ADVERSE EVENTS

All adverse events (AEs) will be coded using the standardized Medical Dictionary for Regulatory Activities (MedDRA) central coding dictionary, version 19.1 or greater. Adverse event analyses will be performed on the mITT and Safety analysis populations.

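### The Safety set inherits an eligibility condition from ITT, so treated patients later found ineligible are, read literally, left out of the adverse event summary tables

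*SAP*

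**What the plan says.** Protocol 12.2.1 sets a broad rule for safety reporting: "Adverse events will be reported for all enrolled subjects through the time of study exit". Enrolled there means having signed consent.

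SAP 6.5 replaces this rule and says so: "this is a change from the protocol, where it states that adverse events will be reported on all enrolled patients". The new set is defined as follows: "Subject will be included in the safety group if they are in the ITT analysis population and study treatment was at least attempted". The stated reason is that the all-enrolled set could understate event rates among patients in whom randomised treatment was attempted. Patients are analysed by treatment received.

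ITT is not simply everyone randomised. SAP 6.2 requires that subjects "have signed the ICF, meet study eligibility criteria, and have been randomized to either the treatment or control arm of the study", and Protocol 12.2.2 has the same condition: "meet study eligibility criteria, and are randomized to the treatment or control arm of the study". SAP 6.3 puts it in mITT as well. SAP 10 then names the sets to be used: "Adverse event analyses will be performed on the mITT and Safety analysis populations".

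SAP 7.4 summarises protocol violations for the ITT set, and one listed violation type is: "Subject did not meet the inclusion and/or exclusion criteria and were enrolled".

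**The concern.** A safety population should contain the patients exposed to the study treatment. Here it is defined through ITT, and ITT carries an eligibility filter. A patient can be randomised, treated and only afterwards found not to have qualified. That patient was exposed, but on the text belongs to neither set used for adverse event tables. Under the protocol's rule the patient's events would have been reported up to study exit.

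At stake are the numerators and denominators of the adverse event and SAE rates by arm. The SAP's two sections on eligibility also point in different directions, so two programmers could build two different Safety sets from the same document.

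**Working it through.** The plan states no figure on this point, so there is nothing to reproduce. The check is one of set definitions, followed by an illustration on assumed rates.

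**Set logic**

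- ITT = consented, eligible and randomised (SAP 6.2).
- Safety = ITT and treatment attempted (SAP 6.5). Hence Safety = consented, eligible, randomised and treatment attempted.
- mITT = consented, eligible and randomised, plus completed monitoring in the Starling arm (SAP 6.3).
- Adverse event analyses use mITT and Safety only (SAP 10).

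Both sets lie inside the eligible group, so a treated but ineligible patient is in neither.

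**Is the case foreseen?** Yes.

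- Protocol 8.7 lists incorrect enrolment as a possible reason for withdrawal.
- Protocol 14.2 and SAP 7.4 list enrolment of an ineligible subject as a deviation or violation.
- Two exclusions in Protocol 8.3 depend on what happens after randomisation: number 12 (study protocol cannot be started inside an hour of randomisation) and number 26 (management departs from the algorithm). The second can arise during treatment.

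**Does the stated reason cover the eligibility condition?** Assume a 15% event rate in treated patients and 10% or 25% of enrolled subjects untreated and event-free. The all-enrolled rate would then be 15% × 0.90 = 13.5% or 15% × 0.75 = 11.25%. The dilution argument is therefore sound, and requiring attempted treatment removes the dilution in full. The eligibility condition adds nothing to that correction; it only removes patients who were treated.

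**Size, on assumptions only.** Let p be the share of treated patients who are ineligible, r the SAE risk in eligible patients, and k the risk ratio of ineligible to eligible patients. None of these is in the documents. Take r = 15%.

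- Reported rate (eligible only) = r
- Rate in all treated = r × [1 + p(k − 1)]
- Gap = r × p × (k − 1)
- Share of patients with an SAE who leave the tables = pk / [1 + p(k − 1)]

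| p | k | Reported | All treated | Gap (points) | Share of SAE patients lost |
|---|---|---|---|---|---|
| 3% | 1.5 | 15.0% | 15.225% | 0.225 | 0.045/1.015 = 4.4% |
| 5% | 2 | 15.0% | 15.75% | 0.75 | 0.10/1.05 = 9.5% |
| 10% | 2 | 15.0% | 16.5% | 1.5 | 0.20/1.10 = 18.2% |
| 5% | 1 | 15.0% | 15.0% | 0 | 5.0% |
| 5% | 0.5 | 15.0% | 14.625% | −0.375 | 0.025/0.975 = 2.6% |

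At the planned 120 subjects, 5% is 6 patients. With k = 2 they would contribute 6 × 0.30 = 1.8 expected SAE patients, out of 114 × 0.15 + 1.8 = 18.9.

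**The case against.** The best defence is that the eligibility condition was meant only as having passed screening, so that a patient randomised in error stays in ITT. Three places support this:

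- SAP 7.4 counts eligibility violations in the ITT set. That row would be empty if ITT held no ineligible patient.
- SAP 6.4 asks only for critical eligibility criteria in the per-protocol set. Taken literally, ITT would be stricter on eligibility than per-protocol.
- Protocol 8.1 and 8.6 remove consented but ineligible subjects as screen failures, and 8.6 places its own checks before randomisation.

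This shows that the intent may have been sound. It does not settle the text, because neither 6.2 nor 6.5 says when eligibility is judged. What it establishes is that the SAP supports two readings and needs one rule.

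Several stronger inferences are tempting, and the documents do not support them:

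- *That the SAP widened the safety set.* It narrowed it, from all enrolled to ITT with treatment attempted.
- *That these patients' events vanish.* The listing of all adverse events (SAP 10.1) and the death listing (SAP 10.3) name no population and may still show them. The loss is from the summary tables, which carry the rates and the comparison between arms.
- *That harm is understated.* This needs a higher event risk in ineligible patients. The documents give no such risk, and some failures, such as missing the 24-hour enrolment window, need not imply one. At equal risk the percentage is unbiased; at lower risk the Safety set over-reports.
- *That the bias is near 10%.* The 9.5% above is an assumed share of SAE patients leaving the tables. The shift in the rate on the same inputs is 0.75 points.
- *That the loss falls mainly on the Starling arm.* The control arm has no required therapeutic protocol (Protocol 7.2), so exclusion 26 could bite unequally. The documents do not say whether it would be used to reclassify patients after randomisation.

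**Conclusion.** The point stands as one about definitions. On the literal text, patients who are randomised, treated and later found ineligible are left out of the adverse event summary tables. The SAP's dilution reason does not justify this, and it conflicts with SAP 7.4.

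The size and direction of any bias in the rates are unknown. On the assumptions shown, the rate gap is about 0.2 to 1.5 percentage points over 3–10% ineligible and 1.5–2 times the risk, is nil at equal risk, and reverses below it. Even with no bias in the percentage, exposed patients and their events leave the tables. The likely effect is modest and the correction costs almost nothing, so this is a free improvement, not a threat to the trial's conclusions.

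**What to change.** In SAP 6.5, define Safety without reference to ITT: all randomised subjects in whom study treatment was attempted, whether or not they were later found ineligible, analysed by treatment received. In SAP 10, make this the primary set for adverse event tables; the mITT table may stay as supplementary. State in SAP 6.2 whether a randomised subject later found ineligible remains in ITT, and bring 7.4 into line.

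The cost is a change of SAP wording, with no new data collection apparent. One limit remains. Protocol 12.2.1 reports events only up to study exit, and Protocol 8.7 allows withdrawal for incorrect enrolment. For a patient withdrawn on that ground, the new set would bring in events up to exit but could not recover later ones.

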## 7 GENERAL ISSUES FOR STATISTICAL ANALYSIS

### 7.1 ANALYSIS SOFTWARE

Analysis data sets, statistical analyses and associated output generated by [REDACTED] will be generated using SAS® Software version 9.4 or later or R version [REDACTED]

3.2.3 or later. [REDACTED] Standard Operating Procedures (SOPs) will be followed in the creation and validation of all analysis datasets, tables, listings, figures and analyses.

## 7.2 DISPOSITION OF SUBJECTS AND WITHDRAWALS

All subjects who provide written informed consent will be accounted for. The number and percent of subjects in each analysis population will be presented, where the percentage is based on the number of enrolled subjects. The number and percent of PP, mITT and ITT subjects who completed each scheduled assessment will be presented. The frequency and percent of PP, mITT and ITT subjects randomized at each investigational site by treatment arm will be presented. A flow chart and listing will also summarize subject accountability.

The number and percentage of subjects prematurely withdrawing from the study will be presented all enrolled subjects by treatment group overall and by reason for premature withdrawal. Descriptive statistics (mean, standard deviation, median, minimum, maximum) of number of days on study will be presented by treatment group.

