8. SUBJECT POPULATION AND SELECTION

8.1 Subject Population

[figure not shown]
Adult subjects with the diagnosis of sepsis and refractory hypotension will be considered as a candidate for the study. A maximum of 210 subjects enrolled and in the analysis population will be included in the study. Subjects will be considered to be enrolled when they or their designated representative sign the informed consent form (ICF).

Subjects who are enrolled will be assigned a subject ID. Subjects that sign the ICF, but are found ineligible will be considered screen failures and will be exited from the study at that time. Enrolled subjects who meet study eligibility will be included in the analysis populations and are further described in **Section 12**.

The diagnosis of sepsis is defined as a known or presumed infection and the presence of 2 or more SIRS criteria as detailed in **Section 8.2**. Refractory hypotension is defined as the presence of hypotension following initial resuscitation with 1L of fluid. After obtaining ICF and confirming that the inclusion and exclusion criteria are met, the Cheetah sensors will be placed and connected to the Starling SV monitor. Useable readings will be confirmed prior to initiating the study data collection period.

A diagram outlining the overall subject enrollment plan is shown below:

Figure 1: Subject Flow Diagram

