14.2 Protocol Deviations

An investigator is not allowed to deviate from the Protocol if the deviation affects subject's rights, safety and wellbeing, or the scientific integrity of the clinical investigation. Under

emergency circumstances, deviations from the protocol to protect the rights, safety and well-being of human subjects may proceed without prior approval of the Sponsor and the IRB.

A protocol deviation is a failure to comply with the requirements specified within this clinical study protocol. Examples of protocol deviations may include enrollment of a study subject who does not meet all of the inclusion/exclusion criteria specified in the protocol and missed study visits without documentation. Each investigator shall conduct this clinical study in accordance with this clinical study protocol, regulatory body regulations, Good Clinical Practices.

All deviations are reviewed and assessed for their impact on subject safety by the Sponsor or designee. The PI and study staff is responsible for knowing and adhering to their IRB reporting requirements.

The protocol deviations for this protocol consist of, but not limited to the following:

- Failure to obtain subject's informed consent prior to any study-related activities;
- Subject did not meet the inclusion and/or exclusion criteria and were enrolled;
- Failure to conduct protocol required clinical test or assessment;
- Failure to complete protocol required assessments within the required time frame
- Failure to report serious adverse events according to protocol requirements.

In the event of any deviation from the protocol, the Investigator will be notified of the site's non-compliance. Corrective actions will be required, if necessary. Continued protocol deviations despite re-education of the study site personnel or persistent protocol deviation may result in termination of the site's study participation. Subjects enrolled at these sites will continue to be followed per the clinical protocol.

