## 6 ANALYSIS POPULATIONS

### 6.1 ALL ENROLLED

Any subject who has signed informed consent will be included in the all enrolled population. Should a subject be considered a screen failure, the reason for failure will be documented and the subject will be exited from the study.

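### The eligibility-violation row in SAP 7.4 is zero by construction, because it is counted in an ITT set that excludes ineligible subjects, and no analysis set holds all randomised subjects

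*SAP*

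**What the plan says.** Four rules interact.

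- **Violation table (SAP 7.4).** "This summary will include the number and percent of subjects (overall and by site) with each violation type for the ITT analysis set". Six violation types are listed. One, carried over from Protocol 14.2, is "Subject did not meet the inclusion and/or exclusion criteria and were enrolled". No split by arm is stated.
- **ITT (SAP 6.2, Protocol 12.2.2).** Besides consent, SAP 6.2 requires that subjects "meet study eligibility criteria, and have been randomized to either the treatment or control arm of the study". The protocol has the same condition: "meet study eligibility criteria, and are randomized to the treatment or control arm of the study".
- **Other sets (SAP 6.1 and 6.3 to 6.5).** The all-enrolled set is defined by consent: "Any subject who has signed informed consent will be included in the all enrolled population". mITT repeats the full eligibility condition. PP asks only that critical criteria be met. Safety is drawn from within ITT.
- **Disposition (SAP 7.2).** "The number and percent of subjects in each analysis population will be presented, where the percentage is based on the number of enrolled subjects". The section also plans PP, mITT and ITT counts by site and treatment arm, a flow chart and listing, and premature withdrawals by treatment group and reason.

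**The concern.** A violation table should show, among other things, how many patients were randomised although they should not have been. Here the set used for the count is defined so that such patients cannot be in it, and a reader of the report would take the zero as a finding.

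The same condition leaves a gap in the patient accounting. The sets run from all consented subjects straight to eligible randomised subjects, with nothing for everyone randomised. This matters because the SAP makes PP the primary efficacy set (SAP 6.4 and 9) and puts a monitoring condition on the Starling SV arm alone. Readers need to see who left each randomised arm from the moment of randomisation, and why.

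**Working it through.** The plan states no figure on this point, so the check is set logic plus illustrations. The arm sizes of 80 and 40 come from SAP 5. All loss counts and screen-failure shares are assumed.

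**1. Eligibility row.** The numerator is the number of subjects who are in ITT and are ineligible. ITT requires eligibility, so this is empty. With k ineligible among 120 randomised:

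| k | SAP 7.4 count | k/120 |
|---|---|---|
| 3 | 0 | 2.5% |
| 6 | 0 | 5.0% |
| 12 | 0 | 10.0% |

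The other five violation types do not depend on eligibility and can be non-zero.

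**2. Randomised to ITT.** Two exclusion criteria in Protocol 8.3 can be judged after randomisation: number 12 (treatment protocol not started within an hour of randomisation) and number 26 (treatment departing from the algorithm). Protocol 7.2 sets no required therapeutic protocol for controls, so number 26 would bear mainly on the Starling SV arm. Suppose 8 of 80 Starling SV subjects, and no controls, are classed as ineligible this way. ITT is then 72 and 40. Retention is 72/80 = 90% against 40/40 = 100%, but the by-arm table in SAP 7.2 starts at 72 and the eligibility row in SAP 7.4 reads 0.

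**3. ITT to mITT.** Suppose instead that ITT is 80 and 40 and that mITT loses 12 Starling SV subjects and no controls. Summing the by-site, by-arm table gives 68/80 = 85% and 40/40 = 100%. This step is recoverable.

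**4. ITT to PP.** PP requires only critical criteria, so it need not nest within ITT. Suppose 8 of 80 Starling SV subjects fail a non-critical criterion (out of ITT, kept in PP) and 8 others leave PP. ITT = 80 - 8 = 72 and PP = 80 - 8 = 72. The counts suggest no loss, although PP holds 72/80 = 90% of those randomised.

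**5. Percentage of enrolled.** If 20% of consented subjects fail screening, 120/0.8 = 150 are enrolled. Losing 12 and 0 gives 108/150 = 72.0%, and losing 8 and 4 also gives 108/150 = 72.0%. Per arm these are 85% against 100%, and 90% against 90%. The pooled figure is likewise the same for both patterns at 10% screen failures (81.0%) and at 40% (54.0%).

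**The case against.** The strongest reply is that SAP 7.2 already covers most of what a reader needs. A reader might infer from the consented-subject denominator that losses from each arm are hidden. The documents do not support that: the same section plans PP, mITT and ITT counts by site and arm, withdrawals by group and reason, and a flow chart and listing. Step 3 shows that a lopsided mITT set would be visible. A reader might also infer that the whole violation table is empty, but only one of its six rows is.

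Nor does Protocol 14.2 turn every screen failure into a deviation, although enrolment is defined by consent. Protocol 14.2 defines a deviation as a failure to comply. Protocol 8.1 provides that "Subjects that sign the ICF, but are found ineligible will be considered screen failures" and are exited, so a subject handled that way is compliant and in any case cannot enter an ITT table.

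It can also be said that ineligible subjects may surface elsewhere. Protocol 8.7 lists incorrect enrolment as a withdrawal reason, and withdrawals are tabulated by arm. This stands in part. Withdrawal for that reason is optional and is not the same as exclusion from an analysis set. The content of the flow chart and listing is not specified, and the table shells that SAP 7.3 places in an appendix are not in the text available. Subjects randomised, judged ineligible and not withdrawn therefore have no specified by-arm count.

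**Conclusion.** The concern holds in a limited form. On the definitions as written, the eligibility row is certain to be zero, whatever the true number. The step from randomised to ITT has no specified by-arm count, and it can be lopsided if exclusions 12 and 26 are applied after randomisation. Whether they would be applied that way is an assumption, because the documents do not say. Losses from ITT to mITT are recoverable by arm. Losses from ITT to PP are largely so, except where PP keeps subjects whom ITT drops. The consented-subject denominator is a lesser fault: it mixes screen failures with losses from the arms and cannot tell equal losses from unequal ones.

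No test, estimate or error rate changes. What is affected is whether the report can show who was removed after randomisation. The percentages above illustrate the mechanism and are not forecasts.

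**What to change.** - **SAP 6:** add an all-randomised set with no eligibility condition.
- **SAP 7.4:** tabulate violations in that set, by arm as well as by site, and let the eligibility row count ineligible subjects who were randomised.
- **SAP 7.2:** report ITT, mITT, PP and Safety as percentages of randomised subjects in each arm, with the reasons for exclusion from each set. Keep consented subjects as the denominator for screen failures only.

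The cost is a short SAP revision, one added population definition and an arm split in the affected tables. No new data are collected, and power and alpha are unaffected.

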## 7.3 METHODS FOR WITHDRAWALS, MISSING DATA, AND OUTLIERS

All reasonable efforts will be made to obtain complete data for all subjects; however, missing observations will occur due to death, loss to follow-up, withdrawal, non-adherence to the protocol, and possible non-evaluable assessments. Since this is unlikely due to the short follow-up time schedule and the consistent nature of data collection, missing data will not be imputed. However, should more than 5% of subjects be missing evaluable data for the primary endpoint, then as a sensitivity analysis to assess the impact of missing data on the primary endpoint treatment comparisons, treatment group comparisons on the primary endpoint will be performed where missing data are first imputed via multiple imputation linear regression using the FCS method in SAS. The multiple imputation model will use, as covariates in the imputation model, the demographic variables shown in the demographics table shell in Appendix A. A total of 10 complete datasets will be created for the multiple imputation and the primary endpoint treatment comparisons will be carried out within each imputed dataset; results will then be combined across imputed datasets using standard multiple imputation techniques in PROC MIANALYZE to obtain one treatment comparison p-value on the primary endpoint. Tables detailing missing data and analysis populations will be provided in the final report. Should the sensitivity analysis be required, it will also be provided in the final report.

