9.3.3 Additional Data Collection

Other data points and associated times will be collected in addition to the analysis of the continuous data from the Starling SV system. Types of data points for collection are:

- Medical history
- Medications
- Volume of treatment fluid administered
- Urine output (to be recorded every 12 hours)
- Respiratory status
- Serum Creatinine level (every 24 hours +/- 4 hours , for 72 hour monitoring period and at 30 day discharge)
- Lactate level (per chart review, if available)
- Significant clinical events not previously identified for study data collection, e.g. cardiac arrest, CPR, intubation, extubation, placement of catheters (intravenous, arterial, urinary, etc), etc.
- Changes in mechanical ventilator status parameters

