12.6 Subject Accountability and Missing Data

Subjects enrolled in this study are followed for a short time period, and missing data in this study is expected to occur at a low rate. All efforts will be used to prevent missing data. These efforts include, but are not limited to, complete site training and regular monitoring to help to minimize missing data.

Subjects without the minimum amount of monitoring [i.e. throughout first 72 hours of study enrollment,] and measurements specified in the protocol will be considered as missing in the final analysis. The impact of missing data on the study will be evaluated via sensitivity analyses if more than 5% of subjects do not have evaluable data for the primary outcome. In the final report, the number and proportion of subjects eligible for and compliant with each analysis population will be presented.

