### 6.3 MODIFIED INTENT TO TREAT POPULATION (MITT)

Subjects will be included in the Modified Intent-to-Treat (mITT) group if they sign the ICF, meet study eligibility criteria, are randomized, and in the treatment group receive monitoring for the first 72 hours of study enrollment or until ICU discharge, whichever occurs first. The mITT population will be conducted as a supportive analysis population for the primary and secondary endpoints.

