### 6.4 PER-PROTOCOL (PP)

Subjects will be included in the Per-protocol group if they sign the ICF, are randomized and have the assigned procedure completed, meet critical study eligibility criteria and have no major protocol deviations (to be pre-defined as an attachment to the interim and final analyses), and, in the treatment group, receive monitoring for the first 72 hours of study enrollment. The PP population represents the primary analysis population for the primary and secondary endpoints.

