# 9 EFFICACY ANALYSES

All efficacy analyses will be performed on the PP analysis population (primary) and mITT analysis population (supportive).

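### SAP 7.3 names no population for the missing-data check, and no planned efficacy analysis restores Starling subjects excluded for incomplete device monitoring

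*SAP*

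**What the plan says.** **Trigger and imputation.** SAP 7.3 does not impute in the main analysis. It adds multiple imputation "should more than 5% of subjects be missing evaluable data for the primary endpoint, then as a sensitivity analysis". Neither the denominator of the 5% nor the dataset to be imputed is named. Protocol 12.6 sets the same threshold, "if more than 5% of subjects do not have evaluable data for the primary outcome", again without a population. It also says that subjects lacking the minimum monitoring "and measurements specified in the protocol will be considered as missing in the final analysis".

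**Efficacy populations.** SAP 9 states: "All efficacy analyses will be performed on the PP analysis population (primary) and mITT analysis population (supportive". The SAP uses ITT for disposition (7.2), protocol violations (7.4) and as the base of the safety set (6.5), but for no named efficacy analysis.

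**Who is removed.** mITT (SAP 6.3) requires that subjects "in the treatment group receive monitoring for the first 72 hours of study enrollment or until ICU discharge, whichever occurs first". PP (SAP 6.4) has a similar condition, "in the treatment group, receive monitoring for the first 72 hours of study enrollment", without the alternative of ICU discharge. Neither places a monitoring condition on controls. PP also requires that subjects "meet critical study eligibility criteria and have no major protocol deviations (to be pre-defined as an attachment to the interim and final analyses", and this applies to both arms.

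**Where the endpoint data come from.** Protocol 9.3.3 says: "Other data points and associated times will be collected in addition to the analysis of the continuous data from the Starling SV system". Its list includes treatment fluid volume and 12-hourly urine output.

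**The concern.** Completing 72 hours of monitoring is a post-randomisation event, and PP and mITT apply it to one arm. The reasons for failing it may be related to outcome. Protocol 8.7.1 lists interrupted data collection, severe agitation and cardiopulmonary resuscitation as grounds for treating a subject as lost. SAP 7.3 itself expects missing data from death, withdrawal and non-adherence.

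The trial asks how fluid balance differs between two randomised strategies. If the Starling subjects who could not be monitored differ in fluid balance from those who could, the PP and mITT comparisons are biased. A missing-data sensitivity analysis is the natural place to see this, but imputation run inside PP or mITT cannot, because those subjects are no longer in the dataset. Some of them may have a complete fluid record that goes unused because a sensor stream stopped.

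**Working it through.** **1. The plan's own figure.** Inputs from SAP 5: 80 Starling and 40 control, effect -2 L, SD 3 L, two-sided 0.05. Standard error = 3 × √(1/80 + 1/40) = 0.581 L, noncentrality = 2/0.581 = 3.44, df = 118. The noncentral t gives 92.7% power, as stated. The plan's inputs are therefore used below.

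**2. What happens to a Starling subject with interrupted monitoring but charted fluid data**

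| Rule | Result |
|---|---|
| Protocol 12.6 | Kept in the count, as missing |
| SAP 6.3 and 6.4 | Not in mITT or PP |
| SAP 7.3 | Population not stated |
| SAP 9 | Analyses run in PP and mITT, so the subject is neither analysed nor imputed |

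The last row does not depend on the trigger's denominator. Counting the 5% over all randomised subjects could make the imputation run, but under SAP 9 it would run on a dataset without this subject.

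**3. Can the trigger stay silent?** The documents give no loss rate, so these rates are assumptions. Let m_T and m_C be the loss in each arm, and s the share of Starling losses that are monitoring failures.

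- Rate over randomised = (80·m_T + 40·m_C)/120
- Rate within mITT = (80·m_T·(1 − s) + 40·m_C)/(120 − 80·m_T·s)

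| m_T / m_C | s | Randomised | Within mITT | Fires in mITT? |
|---|---|---|---|---|
| 10% / 10% | 1 | 12/120 = 10.0% | 4/112 = 3.6% | No |
| 10% / 10% | 0.75 | 12/120 = 10.0% | 6/114 = 5.3% | Yes |
| 10% / 10% | 0.5 | 12/120 = 10.0% | 8/116 = 6.9% | Yes |
| 15% / 15% | 1 | 18/120 = 15.0% | 6/108 = 5.6% | Yes |
| 20% / 10% | 1 | 20/120 = 16.7% | 4/104 = 3.8% | No |

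At 10% per arm, silence needs at least 7 of the 8 Starling losses to be monitoring failures: with 7 removed the rate is 5/113 = 4.4%, and with 6 it is 6/114 = 5.3%. With 8 Starling subjects removed and no other Starling loss, 5 missing controls do not fire the trigger (5/112 = 4.5%) and 6 do (6/112 = 5.4%).

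**4. Possible size of the bias (illustration).** Assume no true effect, SD 3 L, and 10% of Starling subjects excluded (80 − 8 = 72 kept), with a mean balance 0.5 to 1 SD (1.5 to 3 L) above those kept. The size and direction of this offset are assumptions.

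- Shift = excluded share × offset: 0.10 × 1.5 = 0.15 L and 0.10 × 3 = 0.30 L, or 7.5% and 15% of the planned 2 L.
- Standard error with 72 and 40 = 3 × √(1/72 + 1/40) = 0.592 L. Noncentrality = 0.15/0.592 = 0.25 and 0.30/0.592 = 0.51. df = 110, critical value 1.982.
- Chance of a significant result favouring Starling: 4.4% and 7.3%, against 2.5% with no shift.
- With 36 controls observed instead of 40: 4.3% and 7.0%.

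If the excluded subjects had lower balances, the shift would go against Starling.

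**The case against.** **The stronger reading.** A reader might infer that the 5% check is confined to PP and mITT and so sees essentially only control losses. The documents do not support that.

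- SAP 7.3 names no denominator. The causes of missing data that it lists include withdrawal and non-adherence, which PP would largely have removed, so its author may have meant a wider count. On protocol 12.6's reading, the 12/120 example fires.
- Fully monitored Starling subjects who lack fluid data stay in mITT and count.
- PP's deviation and completed-procedure conditions can remove controls too.
- Protocol 12.6 applies its monitoring rule to subjects generally, and protocol 8.1 and 9.2 describe device placement without an arm limit. That controls are exempt is true of the PP and mITT definitions only.

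**Visibility.** Nor should it be inferred that the losses would be hidden. SAP 7.2 requires counts for each population, a flow chart, and withdrawals by arm and reason. SAP 7.3 requires tables of missing data. The exclusions would be seen, but counts do not show what they do to the estimate.

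**Other sensitivity analyses.** SAP 9.1 says fluid balance will also have sensitivity analyses outside formal testing. It specifies neither population nor method, so SAP 9 still governs.

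**Low expected loss.** Protocol 12.6 expects little missing data. If few Starling subjects fail the monitoring condition, the effect is small. This limits the likely size of the problem but does not remove the gap.

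**Conclusion.** The point holds in this form. The population for the SAP 7.3 trigger and imputation is unstated. Under SAP 9 the imputation falls in PP and mITT, which conflicts with protocol 12.6. Starling subjects removed for incomplete monitoring are then never restored, and no specified efficacy analysis tests the effect of that arm-specific exclusion. This part rests on the text alone.

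The silent trigger is conditional. It requires the count to be made within mITT and nearly all Starling losses to be monitoring failures. The bias figures (0.15-0.30 L; 4.4-7.3% against 2.5%) are illustrations that rest on an assumed exclusion rate and on an assumed size and direction of offset. They are not predictions. The documents also do not say whether a Starling death before 72 hours fails the monitoring condition, which would affect how many subjects are excluded.

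The sponsor should correct this before the primary analysis.

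**What to change.** - **SAP 7.3 and SAP 9:** add a sensitivity analysis of the primary endpoint in all randomised eligible subjects (ITT, SAP 6.2), run whether or not 5% is reached. Use the recorded fluid balance for every subject who has one, whatever the device monitoring. Impute only where intake or output data are truly absent, in both arms. State this as an exception to the SAP 9 rule.
- **SAP 7.3:** report missing primary-endpoint data by arm, over ITT.
- **Protocol 12.6 and SAP:** reconcile them so that incomplete device monitoring alone does not make the primary outcome missing in this analysis.

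The analysis must not depend on the 5% gate. In the 10% example, if all eight Starling subjects have charted balances, using them lowers the missing rate to 4/120 = 3.3%. A gated analysis would then never run.

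The cost is wording changes and one extra analysis run, with no new subjects or procedures. The reported missing rate may be higher, or the estimate less favourable.
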